## 2.1. Background

Influenza causes substantial morbidity and mortality worldwide despite available antivirals and vaccines. Influenza is responsible for 226,000 excess hospitalizations and 30,000 to 50,000 deaths each year in the United States (US) alone (Thompson et al. 2003). Effective therapeutics are needed to prevent mortality or morbidity in those afflicted with severe influenza. Human plasma (delivered as Fresh Frozen Plasma units) or human intravenous immunoglobulin (hIVIg) with anti-influenza antibodies have been proposed as treatments for severe influenza (Luke et al. 2006). A limitation with plasma or hIVIg is that large numbers of human plasma donors/units must be screened to identify those few with a higher-than-average haemagglutination inhibition (HAI) titer to multiple strains of influenza. However, recent clinical trials have not shown benefit to hospitalized patients with severe Type A influenza infections treated with human-derived anti-influenza plasma or hIVIg (Beigel et al. 2019, Davey et al. 2019).

SAB Biotherapeutics, Inc., has developed SAB-176 to address the production limitations and lack of clinical efficacy of human-derived plasma or hIVIg. SAB-176 is a unique anti-influenza hIgG containing fully human polyclonal IgG antibodies with extremely high HAI and microneutralization titers against past, current, and potentially future strains of Type A influenza (H1N1/H3N2) and both lineages of Type B influenza (Yamagata/Victoria). SAB-176 is purified from the plasma of immunized Tc bovines that were immunized with a quadrivalent recombinant HA protein vaccine produced in insect cells. The HA antigens match the four influenza strains recommended yearly for the Northern hemisphere by the Center for Disease Control and Prevention.

Furthermore, Tc bovine hIgGs have an IgG1 subclass content of approximately 80-90% versus approximately 60% for human derived IVIg. IgG1 strongly activates complement and effector cells (natural killer cells, neutrophils, monocytes, etc.) of the innate immune system. SAB-176 is therefore much different than human-derived anti-influenza hIVIgs. SAB Biotherapeutics, Inc. believes that SAB-176's distinct attributes, in combination with early treatment of severe influenza disease, could demonstrate that the product reduces morbidity and mortality in patients with Type A and/or B influenza.

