# 6.2. Preparation/Handling/Storage/Accountability

## 6.2.1. Interventional Product / Placebo

SAB-176 is diluted in normal (0.9%) sterile saline under aseptic conditions. The diluted product is intended for administration by the IV route. The dose of IMP will be calculated. The pharmacy will prepare a bag containing the dose of SAB-176 plus as much normal (0.9%) saline as is needed to reach the concentrations for the study. The infusion of SAB-176 (active treatment) or normal saline control (placebo) will be provided in an opaque bag to obscure the bag (as SAB-176 may develop bubbles like IVIg if agitated). The drip chamber will also be covered, but accessible if needed by nursing staff for verification of flow rate, etc. The infusion will continue at a stable rate of up to 2.0 mL/min. Further details can be found in the Investigator's Brochure.

Participants randomised to the control (placebo) infusion will receive normal (0.9%) saline in approximately the same volume as they would have received if randomized to the active arm.

hVIVO will receive supplies of investigational product / placebo after it has had Qualified Person sign off by the Good Manufacturing Practice (GMP) Pharmacy provider and it has been verified ready for dispatch by the unblinded Study Monitor. All investigational product / placebo supplies will be used only for this protocol and for no other purpose.

Ready-to-dispense investigational product / placebo will be supplied by the pharmacy for each quarantine prior dosing. Once received at hVIVO, hVIVO will perform stock level accountability and the investigational product / placebo will be stored at 15 to 25°C securely. Investigational product / placebo accountability will be controlled by hVIVO and monitored by the Study Monitor throughout the study and at study close-out.

The Investigator will ensure that all supplies are received by a responsible person, all deliveries and returns are documented and signed for, and the condition of the investigational product / placebo is monitored. Accurate records will be kept of when and how much investigational product / placebo is dispensed and used in the study. Any reasons for departure from the protocol dispensing regimen will be recorded.

Accountability records will be available for verification by the Study Monitor at each monitoring visit. At the completion of the study, there will be a final reconciliation of all investigational product / placebo.

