#### 8.16.2. Challenge Virus Serology Samples

A participant must be serosuitable to take part in the study, i.e., he/she must have no or low pre-existing serum levels of antibodies specific to the Challenge virus. This antibody titre cut-off for serosuitability will be described in the AP.

Serum levels of pre-existing Virus specific antibodies to the Challenge virus will be determined using HAI influenza or as described in the AP.

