#### 8.17.3. Viral Load

Nasopharyngeal swabs (or nasal washes) will be collected for viral load assays. Viral load may be determined by qRT-PCR and a cell-based infectivity assay (TCID50) if PCR positive, to investigate the following parameters:

- infectivity status and rate.
- viral dynamics (e.g., duration, peak, time to peak).

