#### 8.17.4. Exploratory Analyses

#### 8.17.4.1. Nasal Pharmacokinetics

Nasal sample aliquots (nasosorption / mid turbinate swab) may be processed, stored, and analysed for exploratory PK analysis in accordance with the AP.

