#### 9.4.4. Primary Efficacy Analysis

The main estimator of the primary endpoint, the median VL-AUC of Influenza A/California/2009 H1N1 virus as determined by qRT-PCR on nasal samples (virology), will be analysed on the PP Analysis Set.

The calculation of the VL-AUC will be performed on log10-transformed PCR data using the trapezoidal summation rule based on actual time intervals in hours. Results below the lower limit of quantification (LLOQ) will be given values as detailed in the SAP.

Descriptive statistics and the 95% CI will be presented by treatment group. The difference between the two groups will be analysed using the Wilcoxon rank sum test. The two-sided p-value will be presented.

The primary efficacy analysis will be complemented by the analyses of a supportive estimator (Median VL-AUC of Influenza A/California/2009 H1N1 virus as determined by quantitative viral culture) as well two sensitivity estimators:

- Geometric mean of VL-AUC of Influenza A/California/2009 H1N1 virus as determined by qRT-PCR.
- Geometric mean of VL-AUC of Influenza A/California/2009 H1N1 virus as determined by quantitative viral culture.

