Viral shedding	
 
One or both of the following definitions must be met:
 
At least two positive quantifiable detections by viral load qPCR assay specific for the Challenge virus, reported on two or more consecutive days and from two independent samples (which can either be the same type of sample or different e.g., throat swab and nasal wash or two nasal wash samples).
 
One positive detection by viral load qPCR assay, specific for the Challenge virus, in which an aliquot of the same sample has also tested positive in a viral culture assay appropriate for detecting the Challenge virus.
 

Laboratory confirmed Virus infection	Viral shedding definition has been met.

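### Culture viral load is read in nasal samples that may carry neutralising SAB-176, so culture results cannot separate an effect in the participant from neutralisation after sampling

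*Combined protocol and SAP*

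**What the plan says.** - **Product and control.** Section 2.1 describes SAB-176 as "antibodies with extremely high HAI and microneutralization titers against past, current, and potentially future strains". The control has no antibody: "Participants randomised to the control (placebo) infusion will receive normal (0.9%) saline in approximately the same volume" (6.2.1).
- **Antibody at entry.** Section 8.16.2 says of each participant that "he/she must have no or low pre-existing serum levels of antibodies specific to the Challenge virus".
- **Assays.** "Viral load may be determined by qRT-PCR and a cell-based infectivity assay" (8.17.3), the latter being TCID50 on PCR-positive samples. Note m to the Schedule of Activities (1.2) sends the post-inoculation nasal virology samples to both assays.
- **Drug in the nose.** Nasosorption or mid-turbinate aliquots "may be processed, stored, and analysed for exploratory PK analysis" (8.17.4.1), so nasal drug is foreseen but its measurement is optional.
- **Use of culture.** In 9.4.4, "The primary efficacy analysis will be complemented by the analyses of a supportive estimator", namely median culture VL-AUC; the geometric mean of culture VL-AUC is one of two sensitivity estimators. Section 3 makes culture AUC, peak, duration and culture-confirmed symptomatic infection secondary endpoints.
- **Infection definition.** Appendix 6 (10.6.2) accepts either quantifiable PCR detections from two independent samples on consecutive days, or one PCR-positive sample "in which an aliquot of the same sample has also tested positive in a viral culture assay". Laboratory-confirmed infection defines the ITT-I set (9.3).

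**The concern.** PCR counts viral RNA, whether or not antibody has bound the virus. TCID50 counts virus that can still infect cells. If a post-infusion sample contains SAB-176, antibody can go on neutralising virus after the sample has left the participant, and culture will read low for that reason alone. The saline arm receives no such antibody.

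Two uses of culture are exposed.

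1. **Corroboration.** Agreement between PCR and culture would normally be read as two assays supporting one conclusion. Culture could agree with no effect on virus in the participant.
2. **Infection status.** A participant with a single PCR-positive sample counts as infected if that sample also cultures. If carry-over suppresses culture, this route is harder to meet on SAB-176. That lowers the active-arm infection rate, in favour of SAB-176. It also removes brief shedders from the active arm of ITT-I, which works against SAB-176 in that comparison.

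**Working it through.** **1. The plan's own figure.** Section 9.2 gives 80% power, two-sided 5%, a 60% relative reduction in PCR AUC and an 81% CV in the control arm. In units of the control mean with a common SD:

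n per arm = 2 × (1.960 + 0.842)² × 0.81² / 0.60² = 28.6, so 29.

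The noncentral t gives 79.2% power at 29 and 80.5% at 30 per arm. The stated 30 per arm is reproduced. It concerns the PCR endpoint only, so this point does not alter it.

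**2. Culture AUC, simple illustration.** Assume no true effect, and that the 81% CV also applies to culture AUC. If a fraction f of culture AUC is lost after sampling in the SAB-176 arm alone, the noncentrality is (f / 0.81) × √(30/2) with 58 degrees of freedom:

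| Loss of culture AUC | P(p < 0.05) |
|---|---|
| 0% | 5.0% |
| 10% | 7.6% |
| 20% | 15.6% |
| 30% | 29.2% |
| 40% | 46.9% |

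**3. Culture AUC, by how antibody acts.** The documents give no nasal concentration, EC50 or in-sample loss, so the range below is assumed. With c the antibody concentration in the sample, simple neutralisation lowers the titre by log10(1 + c/EC50). Ratios of 2.2, 9 and 31 give log10(3.2) = 0.5, log10(10) = 1.0 and log10(32) = 1.5.

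The simulation uses 30 per arm, 65% infected (Table 1), no effect in the participant and a two-sided Wilcoxon test at 5%. Assumed: triangular titre curves, peak mean 3.5 log10 (SD 1.2), cut-off 0.5 log10. The ranges in the last column come from two runs.

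| c/EC50 | Fixed loss (log10) | Rejection, loss stays fixed | Rejection, antibody diluted with the virus, binding reversible |
|---|---|---|---|
| 2.2 | 0.5 | 20% | 5–6% |
| 9 | 1.0 | 50% | 7% |
| 31 | 1.5 | 74% | 14–16% |

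The last two columns differ because a TCID50 titration dilutes antibody along with virus. At a titre of 3.5 log10 the loss at the endpoint well is log10(1 + 31 × 10^−3.5) = log10(1.0098) = 0.004, even for the largest ratio. Irreversible neutralisation in the tube before titration would keep more of the loss. With other assumed peaks (2.5 to 4.5 log10, SD 1, cut-off 0.75), fixed losses of 0.5 and 1.0 log10 gave 18–24% and 47–64%.

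**4. Infection rate.** Placebo: 0.65 × 30 = 19.5 infected. The share of infections that qualify only by culture is not in the documents. If it is 10% and all are missed on SAB-176, the active arm reads 0.65 × 0.90 = 58.5% (17.6 of 30). If it is 20%, 0.65 × 0.80 = 52% (15.6 of 30). The chance of a nominally significant difference in favour of SAB-176 is then about 7% and 17%. Missing every such case is the extreme assumption.

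**5. Sampling.** Virology is twice daily on Days 1–7 and once on Day 8: 7 × 2 + 1 = 15 samples, 14 of them after infusion. The nasal PK sample is once daily on Days 1–8, with Day 1 pre-infusion: 7 after infusion, from a different device.

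**The case against.** - **Efficacy conclusions do not rest on culture.** Section 9.1 bases them on the primary analysis and treats other tests as illustrative. Table 6 names no test for any culture endpoint, and infection rates are tertiary. A reader might infer that the trial could declare efficacy on an assay artefact. The documents do not support that: the primary is qRT-PCR VL-AUC on the PP set, which uses neither culture nor infection status. This stands and limits the point to supportive and secondary results.
- **A control may exist elsewhere.** Much of the nasal-sample and assay detail is deferred to the Analytical Plan and site procedures. A reader might infer that none was planned; one can say only that the protocol states none. This stands.
- **Antibody is not exclusive to one arm.** A reader might infer that only SAB-176 samples can contain it. Entry allows low titres, and Appendix 6 defines seroconversion, so placebo participants may also have some. The supportable statement is a difference in level.
- **The size depends on the model.** A reader might take the 50% or 74% rejection rates as expected. They need a loss that survives dilution; the reversible-binding column stays much closer to 5%. This stands, so a range is given.
- **Neutralisation in the nose is a real drug effect.** True. The difficulty is that culture alone cannot separate it from neutralisation after sampling.
- **Either infection route suffices.** Only participants without quantifiable PCR on consecutive days depend on culture, so the bias there is probably small.

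The interpretive gap remains: 9.4.4 offers culture as support for the primary result without this limitation.

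**Conclusion.** The concern holds as a limit on what culture can show. The links are in the protocol: a neutralising product against saline, nasal drug foreseen, shared virology samples, an infectivity readout, and culture used as supportive estimator, secondary endpoints and one route to ITT-I. No stated control separates an effect in the participant from neutralisation after sampling.

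The size cannot be fixed from the documents. With no effect in the participant, rejection for culture AUC ranges from near 5% (antibody diluted out, reversible binding) to about 20–50% (fixed loss of 0.5–1.0 log10). These are illustrations that rest on the assumed curves and losses. The primary analysis, N=60 and the Day 1 pre-infusion sample are unaffected. Bias in infection rates and ITT-I is probably small. This is a worthwhile, inexpensive improvement and does not threaten the main conclusion.

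**What to change.** 1. In 9.4.4 and the SAP, state that culture measures virus recoverable in the presence of drug and is not independent confirmation of the primary result. Cite any carry-over control in the Analytical Plan.
2. For arm comparisons of infection and for ITT-I, add an analysis using only the PCR route (two quantifiable detections on consecutive days) beside the composite definition. State in advance that it takes precedence if the two differ.
3. Report the PCR-to-culture difference by arm. Break it down by nasal titre only if the optional nasal PK is run, noting that this comes from a different sample taken once daily and does not measure antibody in the cultured tube.

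Make these changes before unblinding, as 9.4.1 requires for finalising the SAP. The cost is SAP wording and one added analysis, with no new samples or visits. The downside is that culture results carry less weight and slightly fewer participants count as infected in the PCR-only analysis.

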#### 9.4.5. Secondary Efficacy Analysis

Table 6 summarises the methods for analysis of secondary endpoints. More details will be provided in the SAP.

#### Table 6: Methods for Analysis of Secondary Endpoints

Endpoints	Planned analysis
Peak viral load of VL-AUC of Influenza A/California/2009 H1N1 virus as defined by the maximum viral load determined by quantifiable qRT-PCR measurements in nasal samples starting two days post viral challenge (Day 2) up to discharge from quarantine.	Wilcoxon-rank-sum test (alternative: t-test if underlying assumptions valid)
Duration of influenza quantifiable qRT-PCR measurements in nasal samples.	Wilcoxon-rank-sum test (alternative: t-test if underlying assumptions valid)
Area under the curve over time of total clinical symptoms score (TSS-AUC) as measured by graded symptom scoring system (categorical and visual analogue scales).	t-test if underlying assumptions valid (alternative: Wilcoxon-rank- sum test)
Peak symptoms diary card score: peak total clinical symptoms score (TSS) as measured by graded symptom scoring system (categorical and visual analogue scales).	t-test if underlying assumptions valid (alternative: Wilcoxon-rank- sum test)
Peak daily symptom score: Individual maximum daily sum of symptom score.	t-test if underlying assumptions valid

Endpoints	Planned analysis
	(alternative: Wilcoxon-rank- sum test)
Number (%) of participants with Grade 2 or higher symptoms.	Chi-square test
Incidence of symptomatic infection due to Influenza A/California/2009 H1N1 virus, compared to placebo as measured by: RT-PCR-confirmed symptomatic influenza infection defined as:	Chi-square test (on the composite and each component)

RT-PCR-confirmed influenza infection, AND

Clinical symptoms

	

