#### 2.3.1.1. Risks of SAB-176

SAB-176 is currently concluding a Phase 1 clinical trial (ClinicalTrials.gov identifier: NCT04471038). All participants have been infused with no serious adverse events (SAEs) reported through the highest dose cohort of 50 mg/kg and it appears to be safe and well tolerated. A previous Phase 1 study of SAB-301 (anti-Middle Eastern Respiratory Syndrome virus immunoglobulin) also derived from Tc bovines was shown to be safe and well tolerated at the highest dose of 50 mg/kg (ClinicalTrials.gov identifier: NCT02788188). It is anticipated that the risks for this Phase 2a study will be similar to the Phase 1 studies of SAB-176 and SAB-301 and the use of hIVIg with some unique considerations for proteins of animal origin as discussed below.

Based on hIVIg, common side effects may include:

- headache
- injection site reaction
- nausea
- urticaria
- fatigue
- arthralgia
- pyrexia.

Less common side effects may include:

- vomiting
- back pain
- rash.

Serious side effects seen with hIVIg that could be seen with SAB-176 include:

- Hyperproteinaemia, with resultant changes in serum viscosity and electrolyte imbalances may
  occur in patients receiving IVIg therapy (Steinberger et al. 2003). Humans routinely receive up to
  1 to 2 grams/kg of hIVIg to treat Guillain-Barre syndrome and other immune related neuropathies.
  Therefore, the addition of 50 mg/kg IgG as SAB-176 is a relatively small amount and is unlikely
  to cause AEs related to increased viscosity.
- Aseptic Meningitis Syndrome has been reported with IVIg treatments, especially with high doses or rapid infusion. This risk is anticipated to be minimized given the low amount of protein and relatively slow infusion.
- Haemolysis, either intravascular or due to enhanced red blood cell (RBC) sequestration, can be seen with human IVIg. This risk is anticipated to be low given the lack of exposure of the cows to human RBC antigens.
- Volume overload has been reported with human IVIg. This risk is anticipated to be minimized given the low amount of protein and small total volumes administered.

There may be additional risks of SAB-176 given its animal origin. SAB-176 is a fully human IgG so it is anticipated the risk would be less, though there may be residual animal proteins. The most similar product would be Horse Heptavalent Botulism Antitoxin which is an equine derived non-human polyclonal IgG polyclonal:

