## 6.1. Study Interventions Administered

Participants will be inoculated with an Influenza A/California/2009 H1N1 virus on Day 0. Participants will receive an IV infusion with SAB-176 or placebo on Day 1.

Intervention Name	SAB-176	Placebo	Influenza A/California/ 2009 H1/N1 virus
Туре	Drug	Other	Virus
Dose Formulation	Purified hIgG in a sterile liquid formulated in 10 mM glutamic acid monosodium salt, 262 mM D-sorbitol, 0.05 mg/mL Tween 80, pH 5.5, administered as a liquid solution for injection in 0.9% sodium chloride	Sodium chloride 0.9% solution (normal saline)	Ampoule, Liquid
Unit Dose Strengths	Up to 50 mg/kg	Not applicable	The inoculum virus titre is determined in an infectivity assay, the titre is reported in tissue culture infectious dose (TCID 50 ) per mL (log 10 TCID 50 /mL). The challenge dose is approximately 3.5 x 10  log 10 TCID 50 .
Dosage Levels	A single dose up to 50 mg/kg	A single dose of 0 mg/kg	A single dose of virus will be delivered. Dose volume delivery method is provided in the AP.
Route of Administration	IV infusion	IV infusion	Intranasal
Use	Experimental	Placebo-comparator	Infectious challenge agent
IMP and Non-IMP	IMP	IMP (Placebo)	-
Challenge	-	-	Challenge virus

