# 8.11. Participant Diary Cards

#### Symptom Diary Card (Categorical and Visual Analogue Scale)

Participants will report and assess the severity of any Challenge virus-related symptoms using the hVIVO symptom diary card. This information will be collected using a paper form.

The following symptoms in the 13-item symptom questionnaire will be graded on a scale of 0-3 (Grade 0: No symptoms; Grade 1: just noticeable; Grade 2: clearly bothersome from time to time but does not interfere with me doing my normal daily activities; Grade 3: Quite bothersome most or all the time, and it stops me participating in activities: Shortness of Breath and Wheeze have an additional Grade 4: Symptoms at rest:

- Runny nose
- Stuffy nose
- Sneezing
- Sore throat
- Earache
- Malaise/tiredness
- Headache
- Muscle and/or joint ache
- Chilliness/Feverishness
- Cough
- Chest tightness
- Shortness of breath
- Wheeze

Additional to the categorical symptom diary card, a Visual Analogue Scale dairy card using a 100 mm scale, with the same symptoms, will be completed by the participants.

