# 9.2. Sample Size Determination

Up to 60 participants will be inoculated with the Challenge virus.

The statistical powering selected for this study is estimated to be sufficient for the primary objective and based upon only the primary endpoint. The targeted power for this study's endpoint is for 80% using a two-sided type-one error rate of 5%. The sample size of 60 participants (30 in each arm) will allow detecting a 60% relative reduction in the qRT-PCR-AUC virology with SAB-176 assuming an 81% coefficient of variation in the control arm (taking into consideration Watson et al. 2015, Sloan et al. 2020).

The PCR-AUC data is based on log transformed PCR data.

The sample size indicates the number of participants to be inoculated with the Challenge virus.

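### Symptom efficacy endpoints can be biased against SAB-176, because expected infusion reactions score as influenza symptoms and no scoring window or item split is set

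*Combined protocol and SAP*

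**What the plan says.** - **Comparator.** Section 6.1 gives the placebo as 0.9% saline, and Section 6.2.1 has it infused in about the same volume as the active product.
- **Expected reactions.** Section 2.3.1.1 opens a list with "Based on hIVIg, common side effects may include". The list contains headache, fatigue, arthralgia and pyrexia.
- **Diary.** Section 8.11: "Participants will report and assess the severity of any Challenge virus-related symptoms using the hVIVO symptom diary card". Its 13 items include headache, malaise/tiredness, muscle and/or joint ache, and chilliness/feverishness.
- **Timing.** The Schedule of Activities has the diary three times daily from Day 0. Note q ties only the first Day 1 assessment to the time before infusion.
- **Attribution.** Section 10.3.6.2 takes diary scores above Grade 0 as signs of the challenge infection. They are not also recorded as adverse events unless they meet the AE definition and are judged clinically significant.
- **Analysis.** Table 6 measures peak viral load "starting two days post viral challenge (Day 2) up to discharge from quarantine". None of its symptom rows has a start day, an item split or a rule for reactions, and "Number (%) of participants with Grade 2 or higher symptoms" carries no infection condition. Further detail is deferred to the SAP, whose text is not in the document reviewed.

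**The concern.** SAB-176 is given one day after challenge, inside the period in which symptoms are scored. A headache or aching joints caused by the immunoglobulin goes onto the same card, in the same items, as influenza. Any excess of such reactions can arise in one arm only. Blinding does not help: a blinded participant cannot tell the two causes apart, and the protocol's default is to call the symptom viral.

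Reduction of symptoms is a named secondary objective. If reactions are counted as influenza, a true benefit is diluted. With no true benefit, SAB-176 would look slightly worse than placebo on influenza symptoms. In neither case could the result be read cleanly as an effect on influenza.

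**Working it through.** **The plan's own figure.** Section 9.2 states "The sample size of 60 participants (30 in each arm) will allow detecting a 60% relative reduction", "assuming an 81% coefficient of variation in the control arm", at 80% power and two-sided 5%. In units of the control mean, n per arm = 2 × (0.81 × (1.960 + 0.842) / 0.60)² = 28.6. Dividing by the Wilcoxon efficiency 3/π gives 29.96, that is 30. Power at 30 per arm is 80.5% (noncentral t) to 81.8% (normal). The figure reproduces. It concerns viral load only; the plan gives no figure for any symptom endpoint.

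**Overlap of items.**

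| Expected reaction (2.3.1.1) | Diary item (8.11) |
|---|---|
| Headache | Headache |
| Fatigue | Malaise/tiredness |
| Arthralgia | Muscle and/or joint ache |
| Pyrexia | Chilliness/feverishness |

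**Cards at risk.** If the infusion precedes the second Day 1 card, the post-infusion cards are 2 (Day 1) + 6 × 3 (Days 2 to 7) + 1 (Day 8) = 21. The Day 1 share is 2/21 = 9.5%. A reaction lasting into Day 2 affects further cards.

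**Grade 2 or higher.** Let p1 be the true SAB-176 rate and r the excess share with a Grade 2+ reaction, independent of influenza symptoms. The observed rate is p1 + (1 − p1) × r. Assume 60% on placebo and p1 = 30%. Power is for the chi-square test at 30 per arm, by exact enumeration.

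| r | Observed SAB-176 rate | Observed reduction | Power |
|---|---|---|---|
| 0 | 30.0% | 50% | 66% |
| 5% | 33.5% | 1 − 0.335/0.60 = 44% | 55% |
| 9% | 36.3% | 1 − 0.363/0.60 = 39.5% | 46% |

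The 9% is the headache rate that Section 2.3.1.1 quotes for an equine antitoxin, all severities together. It is probably high for Grade 2+.

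**Other assumptions.** With 45% on placebo and a true relative risk of 0.40, r = 5% and 9% give observed relative risks of 0.49 and 0.56, and power falls from 62% to 47% and 35%. With no true effect at 45%, r = 9% gives (0.45 + 0.55 × 0.09)/0.45 = 1.11.

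**Less exposed endpoints.**
- *RT-PCR-confirmed symptomatic infection.* Take the 65% infection rate in Table 1 and assume that a share s of infected participants is symptomatic anyway. A reaction rate of 9% adds 0.65 × (1 − s) × 0.09: 2.9 points at s = 50%, 0.6 points at s = 90%.
- *TSS-AUC.* A reaction adding 2 points for 24 hours adds 48 score-hours. If 9% are affected, the arm mean moves by 4.3 score-hours over about 168 hours, or 0.026 points on average. The documents give no placebo TSS-AUC to set this against.
- *Peak TSS and peak daily score.* One transient reaction can set the participant's value, and infection is not required. Exposure is of the same kind as for Grade 2+.

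**The case against.** The strongest reply has four parts.

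1. **The size is unsupported.** A reader might infer that the symptom endpoints *are* biased, and that a saline infusion cannot produce these complaints. The documents support neither statement. They give no SAB-176 rate, describe Phase 1 as well tolerated, and contrast 50 mg/kg with the 1 to 2 g/kg at which human immunoglobulin is used. Headache or fatigue can also be reported after saline, so only an excess matters. This stands. For the same reason, reaction rates of 20% or 30% have no source here and are not used.
2. **The window is inferred.** Appendix 6 applies its illness definitions from Day 1, but that rule does not govern the Table 6 endpoints, and the SAP may set a window. Nor does Table 6 define clinical symptoms, so it does not follow that an infusion headache alone would make an infected participant symptomatic. This stands as a limit on certainty. It is also why the window should be written down.
3. **A respiratory reading already exists.** Upper and lower respiratory tract illness are defined endpoints, and without fever, systemic illness needs one of them. True, but they are tertiary and optional (Section 3), so they do not protect a secondary objective.
4. **Little is at stake.** Section 9.1 rests efficacy on the virological primary and treats other tests as exploratory. The bias runs against SAB-176 and so cannot create a false claim of benefit. This stands and limits the importance of the point. It does not make the symptom result interpretable.

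The wording of Section 8.11, which asks for virus-related symptoms, is a weak safeguard: the participant has no means of separating the causes.

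**Conclusion.** The symptom efficacy endpoints can be biased against SAB-176, and the protocol text has no rule that would show whether they are. Exposure is greatest for Grade 2 or higher, peak TSS and peak daily score. It is smaller for TSS-AUC and for RT-PCR-confirmed symptomatic infection. A reader might infer that all symptom endpoints are affected alike; the arithmetic does not bear that out.

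The size is unknown. The illustrative loss of 6 to about 10 percentage points from a 50% reduction rests on assumed Grade 2+ rates, on independence of reactions and influenza symptoms, and on a 5% to 9% excess whose upper end is borrowed from another product at all severities. The primary endpoint and the sample size of 60 are untouched.

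**What to change.** In Section 9.4.5, Table 6 and the SAP, before unblinding:

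1. State the scoring window for every symptom endpoint, and keep the all-item endpoints as they are.
2. Pre-specify two sensitivity versions of Grade 2 or higher, peak TSS, peak daily score, TSS-AUC and the clinical-symptoms component of symptomatic infection:
   - (a) the nine respiratory items only (runny nose, stuffy nose, sneezing, sore throat, earache, cough, chest tightness, shortness of breath, wheeze). Describe these as less affected by infusion reactions, not free of them: Section 2.3.1.1 reports throat discomfort with the equine product and discusses hypersensitivity;
   - (b) all items from Day 2, matching the peak viral load row.
3. State that the all-item result will be interpreted in the light of both.

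The cost is SAP wording and a few tables, since all the data are already collected. Version (a) drops genuine systemic influenza symptoms: Table 1 lists malaise, myalgia and fever as typical of this virus. Version (b) drops genuine Day 1 symptoms and keeps reactions that last into Day 2. Both should therefore be supportive only.
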